16.1 Sample size calculation

No formal sample size calculations have been performed. The sample size of 40 completers is based on EMA guideline⁵.

16.2 Definition of analysis sets

Descriptions and analysis of efficacy will be based on the Full Analysis Set (FAS), as defined in ICH E9 guidelines.²² The FAS includes all patients exposed to N9-GP. The safety analysis and descriptions will be based on the Safety Analysis Set (SAS). The SAS will consist of all patients exposed to N9-GP.

The patients or observations to be excluded, and the reasons for their exclusion must be documented and signed by those responsible before database lock. The patients and observations excluded from analysis sets, and the reason for this, will be described in the clinical trial report.

16.3 Primary endpoint

The primary endpoint is a safety endpoint defined as incidence of inhibitory antibodies against FIX.

The rate of inhibitory antibodies will be reported and a 1-sided 97.5% upper confidence limit will be provided based on an exact calculation for a binomial distribution. For the calculation of the rate the numerator will include the patients with inhibitors, while the denominator will include all

Protocol
 Trial ID: NN7999-3895
 UTN: U1111-1135-9557
 EudraCT No.: 2012-004867-38

~~CONFIDENTIAL~~

| | | |
|----------|------------------|---------------------|
| Date: | 05 November 2019 | Novo Nordisk |
| Version: | 8.0 | |
| Status: | Final | |
| Page: | 98 of 119 | |

patients with a minimum of 10 exposure days plus any patient with less than 10 exposure days but with inhibitors.

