6.4 Withdrawal criteria

The patient may withdraw at will at any time either by the patient or by the patient's parent(s) or the patient's LAR. The patient's request to discontinue must always be respected.

The patient may be withdrawn from the trial at the discretion of the investigator due to a safety concern or if judged non-compliant with trial procedures.

The patient must be withdrawn if the following applies:

1. Dosed in the trial, but not fulfilling the inclusion and/or exclusion criteria
2. Development of FIX inhibitors ≥ 5 BU confirmed by two consecutive tests (central laboratory) and associated with N9-GP binding antibodies (the patient must be withdrawn from N9-GP treatment upon confirmation of FIX inhibitor ≥ 5 BU and attend three inhibitor follow-up visits)
3. Anaphylactic reaction to the trial product, for definition see section [11.1](#)
4. Major surgery prior to 20 EDs. see section [5.3.8](#)
5. Significant thromboembolic event, see Section [11.1](#)
6. Incapacity or unwillingness to follow trial procedures
7. Participation in another clinical trial while participating in this trial

If a patient experiences treatment failure where haemostatic response is rated as poor according to Section [8.6](#), the investigator should consider if it is in the patient's best interest to continue in the trial.

All data collected prior to withdrawal will be used in the trial analyses.

Temporary or permanent discontinuation of treatment with trial product will not lead to withdrawal from the trial.

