8.1.2 Visit 1 – first dosing with N9-GP

Visit 1 will take place after the screening visit (V0) whenever the first treatment of N9-GP is administered, if not already combined with V0.

Before administrating the first dose of N9-GP the FIX inhibitor test for central laboratory must be taken and sent to central laboratory for analysis. In case of subjective signs of illness and/or fever within 48 hours prior to the first injection of N9-GP the dose should be postponed, if possible.

The patient will continue treatment on either:

- **Pre-prophylaxis treatment.** See Sections [5.3.2](#) and [8.1.1.1](#).
- **Prophylaxis treatment.** See Sections [5.3.3](#) and [8.1.1.2](#).

Assessments for V1 are listed in [Table 2–1](#). In case V0 and V1 have been combined into one visit, assessments should only be performed once, but recorded at both visits in the eCRF.

Protocol
 Trial ID: NN7999-3895
 UTN: U1111-1135-9557
 EudraCT No.: 2012-004867-38

~~CONFIDENTIAL~~

| | | |
|----------|------------------|---------------------|
| Date: | 05 November 2019 | Novo Nordisk |
| Version: | 8.0 | |
| Status: | Final | |
| Page: | 40 of 119 | |

Reminders

- Next visit should be scheduled if applicable, see Sections [8.1.1.1](#) and [8.1.1.2](#)
- In case V2 is not planned or performed within 3 months from visit 1 the Investigator must contact the patient's parent(s)/LAR(s) at least every 12 weeks \pm 1week. See Sections [8.8.4](#) and [8.1.10](#).
- Drug accountability of trial product at V1 must be recorded in the IWRS, see Section [10](#)
- Recording of body weight, see Section [8.3.1](#), and dispensing of N9-GP for trial site dosing via IWRS, see Section [10](#).

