8.4.2.2 Antibody assessments

The analysis will be performed at a laboratory selected by Novo Nordisk A/S or at a Novo Nordisk laboratory. The procedures for analyses will follow the recommendations provided by Novo Nordisk A/S. A description of the method will be included in the final report of this trial.

Plasma samples will be collected for assessment of:

- N9-GP binding antibodies
- FIX inhibitors
- HCP antibodies

Antibody samples should be taken according to [Table 2-1](#).

N9-GP binding antibodies

Screening for antibodies is based on assays that are validated according to international recognised guidelines. [14-16](#) Samples measured above the assay cut-point will be subject to a confirmation test. Samples positive in the confirmatory test will be characterised for specificity to N9-GP, rFIX, and PEG. Isotyping of the anti-drug antibodies will possibly also be performed.

Protocol
 Trial ID: NN7999-3895
 UTN: U1111-1135-9557
 EudraCT No.: 2012-004867-38

~~CONFIDENTIAL~~

| | | |
|----------|------------------|---------------------|
| Date: | 05 November 2019 | Novo Nordisk |
| Version: | 8.0 | |
| Status: | Final | |
| Page: | 57 of 119 | |

Samples will be analysed regularly for N9-GP binding antibodies and will be reported to the investigators at the end of the trial, or when considered relevant. A positive binding antibody sample will not by itself call for any action, but will be part of the continuous evaluation by sponsor of patient safety and treatment efficacy. In case of clinical suspicion of reduced treatment efficacy, an unscheduled visit must be scheduled by the investigator for measurement of FIX inhibitors, N9-GP binding antibodies and peak/trough FIX activity respectively.

FIX inhibitors

A FIX inhibitor test is defined as positive if the titre is ≥ 0.6 BU.

A patient has inhibitory antibodies (inhibitor) if tested positive for inhibitors (≥ 0.6 BU) at two consecutive tests performed at the central laboratory and also tested positive for N9-GP binding antibodies.

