If the result of an inhibitor test is positive, a second confirmatory inhibitor test should be performed by the central laboratory (except for the visit 1 sample that will not need to be confirmed). The confirmatory samples should be collected between 1 and 4 weeks after the first positive inhibitor test, but no sooner than 7 days after the last dose of N9-GP. Sampling for assessments of FIX activity (trough and recovery), N9-GP binding antibodies and lupus anticoagulant must also be performed at the same time.

If the result from the lupus anticoagulant test is positive and N9-GP binding antibody test is negative the patient is considered inhibitor negative and can continue in the trial. If the result from the lupus anticoagulant test is positive and N9-GP binding antibody test is positive the patient is considered inhibitor positive.

The confirmatory test will define the level of inhibitors. Inhibitors will be considered as low titre between 0.6 BU and < 5 BU and high titre ≥ 5 BU.

If a patient has a confirmed high titre inhibitor N9-GP treatment must be stopped and inhibitor follow-up visits must be planned, see Section [8.1.11](#).

If FIX inhibitor development is suspected during the course of the trial due to for instance increased number of bleeding episodes, bleeding episodes difficult to treat, recovery and trough levels below expected values or a positive local inhibitor test, the patient must attend an unscheduled visit as soon as possible and a plasma sample must be shipped to a central laboratory for inhibitor analysis.

If an investigator decides to perform inhibitor testing locally, he/she must send a duplicate sample for inhibitor testing at a central laboratory. The results from the central laboratory will be used in the analysis of trial data. A positive inhibitor test must always be reported as a MESI irrespective of the test being performed locally or at the central laboratory (refer to Section [11.2](#), [11.1](#)).

Protocol
 Trial ID: NN7999-3895
 UTN: U1111-1135-9557
 EudraCT No.: 2012-004867-38

~~CONFIDENTIAL~~

| | | |
|----------|------------------|---------------------|
| Date: | 05 November 2019 | Novo Nordisk |
| Version: | 8.0 | |
| Status: | Final | |
| Page: | 58 of 119 | |

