16.4.2.5 Safety endpoints

Adverse events including SAEs, MESI and development of HCP antibodies

Treatment emergent AEs (TEAEs, defined as AEs occurring after dosing with trial product) and treatment emergent SAEs (TESAEs) will be summarised by frequency of events and frequency of patients with any event. Similar summaries cross-classified by severity and by causal relation to trial product will also be made.

MESIs will be summarised similarly to AEs.

Furthermore, listings will be provided displaying all TEAEs and TESAEs including pertinent clinical information.

HCP antibodies will be listed.

Protocol
 Trial ID: NN7999-3895
 UTN: U1111-1135-9557
 EudraCT No.: 2012-004867-38

~~CONFIDENTIAL~~

| | | |
|----------|------------------|---------------------|
| Date: | 05 November 2019 | Novo Nordisk |
| Version: | 8.0 | |
| Status: | Final | |
| Page: | 100 of 119 | |

All additional safety parameters such as laboratory parameters, including calculation of estimated glomerular filtration rate (eGFR), and physical examinations, including neurological assessments, will be summarised and listed.

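### Could an inhibitor already present before the first N9-GP dose be counted in the primary inhibitor rate?

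*Protocol*

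**What the plan says.** Section 16.3 of the protocol defines the primary endpoint as the incidence of inhibitory antibodies against FIX. It reports a rate with a one-sided 97.5% exact binomial upper limit. On the count it says "For the calculation of the rate the numerator will include the patients with inhibitors". The denominator is every patient with at least 10 exposure days, plus any patient with fewer who has an inhibitor.

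Section 8.4.2.2 defines the case: a titre of at least 0.6 BU "at two consecutive tests performed at the central laboratory and also tested positive for N9-GP binding antibodies". A positive test is to be confirmed, "except for the visit 1 sample that will not need to be confirmed". On the binding-antibody assay the same section adds: "Samples positive in the confirmatory test will be characterised for specificity to N9-GP, rFIX, and PEG".

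Before the first dose, Section 8.1.2 requires that "the FIX inhibitor test for central laboratory must be taken and sent to central laboratory for analysis". Nothing there says that the result is awaited. Exclusion criterion 7 (Section 6.3) rests on medical records. Inclusion criterion 4 (Section 6.2) allows up to 3 exposure days to FIX products and 5 to blood components.

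The SAP covers the neurocognitive data only (SAP Section 6) and adds no rule for inhibitors.

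**The concern.** An incidence should count new cases, and the trial exists to learn whether N9-GP provokes inhibitors. Yet neither the counting sentence nor the case definition asks for a negative pre-dose test or for onset after dosing. Elsewhere the protocol does write such a condition: Section 16.4.2.5 speaks of "TEAEs, defined as AEs occurring after dosing with trial product". The one sample that would separate old from new inhibitors is compulsory but has no stated role in the analysis.

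A minimally exposed child with an inhibitor that nobody had recorded would pass exclusion 7. He could then be dosed, test positive twice with binding antibodies, and enter the numerator. Withdrawing him later would not take him out, because Section 6.4 says: "All data collected prior to withdrawal will be used in the trial analyses". The inhibitor rate is the primary endpoint and one of only two results given a confidence interval (Section 16), and the denominators are small, so a single patient is visible in it.

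**Working it through.** **1. The text side by side.** The counting sentence in Section 16.3 and the case definition in Section 8.4.2.2 set no onset condition, so the literal gap is there. The surrounding text points one way. Section 16.3 calls the endpoint an incidence. Withdrawal criterion 2 in Section 6.4 and the rationale for exclusion 7 in Section 6.6.2 both speak of inhibitors developing. Section 8.4.2.2 treats the Visit 1 sample differently from on-treatment samples by exempting it from confirmation.

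**2. What must hold for a patient to be miscounted.** All of the following, in the same patient:

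- an inhibitor present before the first N9-GP dose, in a child with at most 3 FIX and 5 blood-component exposure days, or none;
- no trace of it in the medical records;
- persistence after dosing;
- two consecutive central results of at least 0.6 BU;
- a positive N9-GP binding-antibody test.

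**3. Effect of one such patient.** The plan states no expected rate or power (Section 16.1), so there is no planned figure to reproduce. The stated method gives an upper limit equal to the 0.975 quantile of a Beta(x + 1, n − x) distribution for x cases in n patients. For x = 0 this is 1 − 0.025^(1/n); for example 1 − 0.025^(1/39) = 9.03%. The values 20 and 40 are the floors for the main and updated reports (Section 16), and 60 is the number planned to start trial product (Section 6.1).

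| Situation | All confirmed inhibitors counted (upper limit) | Pre-existing case removed (upper limit) | Difference in limit |
|---|---|---|---|
| Only case, n = 20 | 1/20 = 5.0% (24.87%) | 0/19 = 0% (17.65%) | 7.22 points |
| Only case, n = 40 | 1/40 = 2.5% (13.16%) | 0/39 = 0% (9.03%) | 4.13 points |
| Only case, n = 60 | 1/60 = 1.67% (8.94%) | 0/59 = 0% (6.06%) | 2.88 points |
| Plus one that arose after dosing, n = 40 | 2/40 = 5.0% (16.92%) | 1/39 = 2.56% (13.48%) | 3.44 points |

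**4. How likely it is.** The documents give no frequency. Suppose each patient has probability p of meeting every condition in step 2. The chance of at least one among n is 1 − (1 − p)^n. For p = 0.1%, 0.5% and 1% this is 2.0%, 9.5% and 18.2% with 20 patients; 3.9%, 18.2% and 33.1% with 40; and 5.8%, 26.0% and 45.3% with 60. These values of p are assumptions only. One p for everyone also ignores that wholly untreated patients are eligible. The figures show how the chance scales and are no forecast.

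**5. What a stricter rule would cost.** Taking baseline-positive patients out of the rate would rest on a single, unconfirmed Visit 1 result. For on-treatment positives, Section 8.4.2.2 relies on a confirmatory test and on lupus anticoagulant testing alongside it: "If the result from the lupus anticoagulant test is positive and N9-GP binding antibody test is negative the patient is considered inhibitor negative". Visit 1 has neither, so a safety count would be reduced on weaker evidence than is needed to add to it. If the removal also required specificity for rFIX, it would use a condition that the case definition itself does not contain. Where a baseline positive does not persist, removal only shrinks the denominator: 0/40 (upper limit 8.81%) becomes 0/39 (9.03%). Two counts given equal standing would leave no single primary estimate.

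**The case for a change.** The strongest argument for a written rule is that the word incidence is only a label, while the counting sentence is the operational instruction. Section 16.2 lets patients or observations be excluded if this is documented before database lock, but it gives no criterion for this situation, so the choice would be made with the case in view. The definition can even be read more widely: a positive Visit 1 result followed by a positive first post-dose result might pass as two consecutive tests. Both the pre-dose inhibitor sample and the pre-dose binding-antibody sample are already taken, so a rule would cost only a few sentences.

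The textual part of this stands: no onset clause exists, and neither eligibility nor withdrawal supplies one. The claim that the result is therefore open to quiet manipulation does not. The literal count is determinate: every confirmed inhibitor is included. Departing from it would need the signed documentation that Section 16.2 requires, and a description in the trial report. Each confirmed inhibitor is always a serious adverse event (Section 11.1) and prompts a safety committee meeting (Section 11.6.1), so such a case would be looked at individually with its Visit 1 result to hand. A rule written now would also be an addition during the trial: first patient first visit was in July 2014, and footnote 21 of Table 2-2 allows for patients already past Visit 28. It would thus share some of the after-the-fact character it is meant to prevent.

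**Conclusion.** No change is called for. The protocol leaves out a detail that its own vocabulary and sampling schedule let analysts fill sensibly. They count confirmed inhibitors as written and, should a patient's pre-dose Visit 1 sample prove positive, say so beside the rate. Counting every confirmed inhibitor, without judging what caused it, is a defensible primary safety summary.

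If such a patient occurred and was the only case, the upper limit would be higher by about 7 percentage points at n = 20, 4 at n = 40 and 3 at n = 60. That is visible, but always in the cautious direction, and no success criterion or stopping threshold in the documents uses the inhibitor rate. The conclusion assumes that the event is rare, which the limit on prior exposure and the list of joint conditions make plausible but which the documents do not quantify. It also assumes that the compulsory Visit 1 inhibitor result is available when the report is written.

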Novo Nordisk A/S will be responsible for the statistical analysis.

The main statistical reporting of the trial will be performed when at least 20 patients have completed main phase (minimum 50 weeks) with at least 50 EDs and completed visit 23. Data from patients not yet having completed main phase and data from patients that have entered extension phase at this point will be included up to latest visit prior to this cut-off date. The data will be presented for the main phase and extension phase separately as well as combined. Except for the confidence interval for inhibitor rate and for annualised bleeding rate, the evaluation of data will be based on descriptive statistics, i.e. summary tables, listings and figures.

An updated statistical reporting of the trial with supportive data will be performed when at least 40 patients have had at least 100 EDs. Data from all patients will be included up to latest visit prior this cut-off date. The data will be presented for the main + extension phase and the extended prophylaxis period (beyond 100 EDs) separately as well as combined.

All data will be reported separately in a final report when the trial is completed.

[figure not shown]

Figure 16–1 Individual patient flow and time period for main trial report

Protocol
 Trial ID: NN7999-3895
 UTN: U1111-1135-9557
 EudraCT No.: 2012-004867-38

~~CONFIDENTIAL~~

| | | |
|----------|------------------|---------------------|
| Date: | 05 November 2019 | Novo Nordisk |
| Version: | 8.0 | |
| Status: | Final | |
| Page: | 97 of 119 | |

Multiple bleeding locations occurring from the same event (e.g. due to a fall) or at the same time point will be counted as one bleeding episode.

All bleeding endpoints will be evaluated based on bleeding episodes treated with N9-GP unless the bleeding was considered clinically insignificant (non-treatment requiring bleeding episode) and the associated treatment given was part of prophylaxis.

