16.6 Interim reporting

All data from main phase of the trial will be analysed and reported when minimum 20 patients have completed main phase with at least 50 EDs and completed visit 23. This report will cover all endpoints and will form the basis for the paediatric indication. Data from patients that have entered extension phase at this point will be included up to latest visit prior this cut-off date. The data will be presented separately for the main phase and extension as well as combined. The main conclusion from the trial will be drawn based on the main phase data.

Furthermore, interim analyses may be performed in association with marketing authorisation applications or in connection with Health Authorities e.g. FDA, EMA and PMDA requirement for/during the regulatory review or to obtain safety data.

An updated report with supportive data will be made when minimum 40 patients have had at least 100 EDs. A final report with supportive data will be made when all patients have completed both parts of the trial.

Protocol
Trial ID: NN7999-3895
UTN: U1111-1135-9557
EudraCT No.: 2012-004867-38

~~CONFIDENTIAL~~

| | | |
|----------|------------------|---------------------|
| Date: | 05 November 2019 | Novo Nordisk |
| Version: | 8.0 | |
| Status: | Final | |
| Page: | 101 of 119 | |

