## 6. Introduction

This Statistical Analysis Plan (SAP) contains a more technical and detailed elaboration of the principal features of the analysis described in the NN7999-3895 Study Protocol related to neurocognitive assessments and includes detailed procedures for executing the statistical analysis of the neurocognitive assessment data.

The SAP is finalized and signed prior to database lock. For operational efficiency, an earlier time is usually targeted. If needed, revisions to the approved SAP may be made prior to database lock. Revisions will be version controlled.

Any changes from the analyses planned in the SAP will be justified in the statistical report.

Prior to database lock, a dry run analysis will occur.

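### The primary inhibitor rate is a crude proportion with no exposure horizon, and beyond a descriptive split by phase nothing estimates inhibitor incidence by exposure days

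*Protocol*

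**What the plan says.** Protocol Section 16.3 reports the inhibitor rate with an exact binomial one-sided 97.5% upper limit. The rule is that "the numerator will include the patients with inhibitors, while the denominator will include all", and the denominator is completed as "patients with a minimum of 10 exposure days plus any patient with less than 10 exposure days but with inhibitors". No ED horizon is attached.

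The opening of Section 16 sets the main report at 20 patients with at least 50 EDs, and adds: "Data from patients not yet having completed main phase and data from patients that have entered extension phase at this point will be included". For each of them the data run to the last visit before the cut-off. For the update at 40 patients with at least 100 EDs: "Data from all patients will be included up to latest visit prior this cut-off date". Results are shown by phase and combined. The main phase ends at Visit 23 (ED 50) and the extension at Visit 28 (ED 100). Section 16.6 adds: "The main conclusion from the trial will be drawn based on the main phase data".

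For safety events, Section 16.4.2.5 plans summaries, and "listings will be provided displaying all TEAEs and TESAEs including pertinent clinical information". It also plans summaries and listings of additional laboratory parameters. The SAP does not extend the inhibitor analysis: it "contains a more technical and detailed elaboration of the principal features of the analysis described in the NN7999-3895 Study Protocol related to neurocognitive assessments".

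**The concern.** The 20 × 50-ED and 40 × 100-ED conditions trigger reports. They are not horizons that each patient must reach. At the main report, an inhibitor-free child at ED 10 carries the same weight as one at ED 50. The phase split keeps events after about ED 50 out of the main-phase display, but it leaves patients with 10–49 EDs in the denominator, and no phase-specific denominator is defined.

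The protocol's own standards point the other way. Section 5.2 treats 100 EDs as the exposure needed to study immunogenicity. Section 16.4.2.1 adjusts the bleeding rate for treatment duration. The primary endpoint has no counterpart to either.

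This is the only primary endpoint and one of two results given a confidence interval or limit. If many inhibitor-free patients are still at low exposure, the rate and its limit will look somewhat better than the data support at the trial's own 50- and 100-ED milestones.

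**Working it through.** The plan states no expected rate, target limit or power, so there is no figure of its own to reproduce. The check applies the planned estimator and compares it with the limit at a stated ED.

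**Inputs from the protocol.** One-sided 97.5% exact limit and 10-ED floor (16.3); 20 patients at 50 EDs (16); 60 planned to start, 40 expected to complete (6.1); planned last first visit 30-Sep-2020 and end of trial 30-Oct-2022 (7).

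**Assumptions, because the documents give no exposure distribution or hazard.** Short patients are evenly spaced over the stated ED range. Risk accrues evenly over the first *h* EDs and stops there, with *h* equal to the horizon (even risk) or to 20 (early risk).

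**Planned limit with zero inhibitors.** 1 − 0.025^(1/n): n = 25 gives 13.7%; n = 30 gives 11.6%; n = 40 gives 8.8%; n = 60 gives 6.0%.

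**Limit at the horizon with zero inhibitors.** Let f_i = min(ED_i/h, 1) be the share of the risk period patient *i* has passed. Solve ∏(1 − p·f_i) = 0.025 for *p*.

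| Report | Patients | Planned limit | Even risk to horizon | All risk in first 20 EDs |
|---|---|---|---|---|
| Main, by ED 50 | 20 at 50 EDs + 5 over 10–49 | 13.7% | 14.9% | 14.0% |
| Main, by ED 50 | 20 at 50 EDs + 10 over 10–49 | 11.6% | 13.3% | 11.9% |
| Main, by ED 50 | 20 at 50 EDs + 20 over 10–49 | 8.8% | 11.0% | 9.1% |
| Final, by ED 100 | 50 at 100 EDs + 10 over 10–99 | 6.0% | 6.4% | 6.0% |
| Final, by ED 100 | 40 at 100 EDs + 20 over 10–99 | 6.0% | 7.0% | 6.0% |

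**Expected crude rate for an assumed true 5%.** This is 5% × mean(f_i). Main report with 20 short: 5% × 0.795 = 4.0% (even risk) or 5% × 0.963 = 4.8% (early risk). Final report with 20 short: 5% × 0.848 = 4.2% or 5% × 0.987 = 4.9%.

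**Last entrant.** 30-Sep-2020 to 30-Oct-2022 is 760 days, or 760/7 = 108.6 weeks. Weekly dosing from the first day gives 109 EDs. A late entrant falls short of 100 only with a slow start: for example, a first dose 10 weeks after screening, then weekly dosing, gives 99.

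**One inhibitor, assumed at ED 30, among 40 patients.** Twenty reach ED 50 inhibitor-free, and 10 of the other 20, including the case, have at least 30 EDs.

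- Planned rate: 1/40 = 2.5%, limit 13.2%.
- Kaplan-Meier at ED 50: 30 at risk at ED 30, so 1/30 = 3.3%. With S = 29/30 the standard error of log(−log S) is 1.00, and the upper limit is 1 − exp(−exp(log(−log S) + 1.96 × 1.00)) = 21.4%.
- Binomial among the case plus those tested at or beyond ED 50: 1/21 = 4.8%, limit 23.8%.

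**The case against.** The strongest reply is that the effect is small and that nothing turns on it. Section 16.1 says: "No formal sample size calculations have been performed". No threshold or test uses the rate either. That stands.

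Even risk over 50 or 100 EDs is also an assumption without support in the documents. What they offer indirectly points to early risk: Section 5.3.5 puts allergic and anaphylactic risk highest in the first 20 EDs, and Section 3.4 links allergic reactions to inhibitors. In the early-risk column the planned limit moves by at most 0.3 points. That argues for a small effect but does not settle it, because neither section says inhibitor risk ends at ED 20 and testing continues throughout.

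At the final report the design itself limits the shortfall. Section 8.1.9 places the end-of-trial visit after at least 100 EDs unless the patient is withdrawn, Section 6.5 allows replacement, and non-completers need not be below 100 EDs. Twenty short patients is an adverse case. Below 10 EDs the rule leans the other way, since cases count and inhibitor-free patients do not.

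A reader might infer that the plan ignores exposure altogether, or that its output would hide the position. The documents do not support that. The phases are defined by EDs, events are listed with clinical detail, and inhibitor tests fall at ED-numbered visits. What is missing is an estimate of incidence by exposure, with numbers at risk.

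**Conclusion.** The point holds as a modest improvement to the primary analysis. Section 16.3 gives a crude proportion without an ED horizon, the main report admits patients with 10–49 EDs, and neither document plans an estimate of inhibitor incidence by exposure beyond the descriptive phase split.

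On the assumed exposure patterns with no inhibitors, the planned main-report limit is too low by 1.2 to 2.2 points under even risk and by about 0.3 under early risk. At the final report the gap is between nil and 1.0 point. It is nil if nobody is short of the horizon.

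A reader might infer a much larger bias. If 40 extra patients all stood at exactly ED 10 under a constant hazard, the expected crude rate would be 2.35% against a true 5%. Nothing in the documents suggests that distribution, so it is not evidence of serious understatement.

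**What to change.** In Section 16.3:

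1. Keep the binomial rate and exact limit as the primary result.
2. Beside it, report Kaplan-Meier cumulative inhibitor incidence on the N9-GP ED scale at 20, 50 and 100 EDs, censored at the last inhibitor test. Give numbers at risk and, when there are events, a one-sided 97.5% log-log upper limit.
3. At 50 and at 100 EDs, also report an exact binomial rate and limit. The numerator is inhibitors arising by that ED. The denominator is those patients plus all patients tested at or beyond it. Label it a conservative bound. It is the only added limit when there are no events, and it overshoots: 0/20 gives 16.8%, where the even-risk value with 20 short patients is 11.0%.
4. State that censoring assumes non-informative withdrawal. This may fail, because anaphylaxis is a withdrawal criterion (Section 6.4) and allergic reactions correlate with inhibitors (Section 3.4). List withdrawals for anaphylaxis or allergic reaction with their last inhibitor test.
5. State that EDs in Section 16 are N9-GP exposure days. Section 5.3 defines them so, but the abbreviation lists in both documents count any factor IX or blood component.

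The cost is wording and one extra output. Inhibitor tests, N9-GP dosing dates and withdrawal reasons are already collected. The downside is wider and possibly less favourable limits, as the one-inhibitor example shows (21.4% and 23.8% beside 13.2%).
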